## **Change from Baseline**

Post-Dose Visit Value – Baseline

• Unless otherwise specified, the baseline definitions specified in Section 5.2 will be used for derivations for endpoints / parameters.

## 12.6.2. Study Population

## **Demographics and Baseline Characteristics**

#### Age

- Age, in whole years, will be calculated with respect to the subject's Baseline visit.
- GSK standard IDSL algorithms will be used for calculating age where birth date will be imputed as follows:
  - Any subject with a missing date and month will have this imputed as '30th June'.
- Birth date will be presented in listings as 'YYYY'.
- Completely missing dates of birth will remain as missing, with no imputation applied.
   Consequently, the age of the subject will not be calculated and will remain missing.

#### **Body Mass Index (BMI)**

• Calculated as Weight (kg) / Height (m)

#### **Hepatitis Status**

- Hepatitis C status will be determined using antibody and/or hepatitis C virus (HCV) RNA assessments performed during screening or during the conduct of the study.
- If both antibody and virus RNA assessments are available, then the latter will take precedence and positive/negative status will be based on whether HCV RNA is detectable (i.e., ≥ limit of quantification) or not.
- A participant will be considered positive for hepatitis B virus (HBV) if they have a positive surface antigen or detectable HBV DNA result. "HBV DNA DETECTED" in the lab comment takes precedence over HBV DNA test result for positive hepatitis B status, for example, if a participant has HBV test result below level of detection, however, the lab comment shows that HBV DNA detected, this participant will be considered positive for hepatitis B. If HBV DNA result is available, it will be used to qualify hepatitis B status as positive or negative (positive if ≥ limit of quantification); otherwise Hepatitis B status will be determined using the surface antigen result.
- Hepatitis status at entry will be based on the assessments prior to/on the start of the study treatment.

#### **Demographics and Baseline Characteristics**

## **Lipid-modifying Agents**

- The following ATC codes correspond to lipid-modifying agents:
  - ATC Level 2: C10
  - ATC Level 3: C10A, C10B (if Level 2 is not available)
  - ATC Level 4: C10AA, C10AB, C10AC, C10AD, C10AX, C10BA, C10BX (if level 2, 3 are not available)
- Participants are considered to have used a lipid-modifying agent at baseline if they are taking the medication at the time of their baseline fasting lipid testing date.
- Participants are also considered to have used a lipid-modifying agent at baseline if they stopped their lipid modifying medication within 12 weeks prior to their baseline fasting lipid testing date.

## **Extent of Exposure**

Exposure to CAB LA +RPV LA injection and to DTG + RPV oral will be calculated from the IP eCRF pages.

#### CAB LA + RPV LA:

- Exposure = Number of IP injections received during Maintenance Phase.
- Overall exposure to IP = min(Date of Latest Maintenance Phase visit, max(Date of Last Injection + 67, Date of Last Dose of Oral CAB+RPV)) – Date of First Study Injection + 1 Note: Last Injection and/or Last Dose of Oral CAB+RPV are only applicable to those who permanently discontinued study treatment.

#### DTG + RPV:

- Exposure = IP Stop Date IP Start Date + 1
- Overall exposure to IP = min(Date of Latest Maintenance Phase visit, Date of Last Dose of DTG + RPV) – Date of First Dose + 1
- There will be no adjustments to the exposure duration for any missed doses.

Duration of dosing in subject years will be calculated as the sum of subject duration of dosing in days (across all subjects)/365.25.

Subjects who were enrolled but did not report an IP start date will be categorised as having zero days of exposure.

For DTG + RPV arm, missing IP discontinuation date will be imputed, for purposes of calculating exposure, as the date of last visit or the recorded date of withdrawal/completion, whichever is earlier.

## Adherence to CAB LA + RPV LA Injection Schedule

Timeliness of Injections relative to Date of Projected Dosing Visits is assessed by using "actual injection visit date - projected visit date from first injection". The injections of interest in adherence analysis are those after first injection. Each injection visit is counted only once. Individual CAB and RPV injections administered at the same visit are not counted twice. "Extra" unscheduled injections are excluded from all derivations. For example, if during a scheduled visit a participant receives 1 ml

of injection instead of 3 ml due to a dosing error, but this participant returns one week later for the remaining 2 ml injection, then the additional visit is excluded. If a participant receives an extra injection at an unscheduled visit by mistake, this visit will also be excluded.

The planned interval is 60 days for the CAB LA + RPV LA arm. Relative days between two planned consecutive visits for injections relative to the planned interval will be calculated as below:

Relative Days=Actual number of days between adjacent injections – 60.

For example, if the time interval between two scheduled consecutive visits for injections is 55 days then relative days = 55 - 60 = -5; if the interval is 60 days then relative days = 65 - 60 = 5 The relative days will be grouped as below:

```
<-14 days
-14 to -8 days
-7 to -4 days
-3 to -2 days
-1 day
0 days
1 day
2 to 3 days
4 to 7 days
8 to 14 days
>14 days
Missed Injection without Oral Bridging
```

Missed Injection with Oral Bridging

In the case that a scheduled injection visit is missed, the time interval between the preceding and the subsequent scheduled injection will be calculated. For example, if Month 8 injection is missed, then the number of days between the actual Month 6 and Month 10 injections will be calculated. To calculate the proportion of injection intervals for each of the above category of relative days, the denominator is the total count of time intervals between adjacent injection visits for CAB LA + RPV LA arm.

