## 12.3. Appendix 3: Assessment Windows

## 12.3.1. Definitions of Assessment Windows for Analyses

Laboratory data, vital signs, ECGs, health outcomes assessments, and genotypic/phenotypic data will be assigned to assessment windows according to actual dates rather than the nominal visit labels as recorded on the eCRF or in the laboratory database.

In most cases the window around an assessment will include all dates from the midpoints between the target day and that of the previous and the proceeding visits. In general, the nominal target study day for Month m is ((m-1)\*30)+1 for Q2M and (m\*30)+1 for DTG + RPV.

For parameters which are not scheduled to be assessed at particular visits, the all-inclusive assessment windows will still be used; however, data summaries will only report scheduled visits. Assessments at unscheduled visits will be included for 'any time On-treatment' time points and in data listings, as well any algorithms that make use of additional data (e.g., Snapshot).

Prior to visit slotting, assessments are first assigned to a study phase (maintenance, and Long Term Follow Up) based on the Tables in Section 12.4.1 and treatment state based on Section 12.4.2.

Maintenance phase assessments other than health outcomes are assigned based on Maintenance Phase Study Day, as shown in Table 6, Table 7, Table 8 and Table 9. The analysis visits from Month 2 to Month 12 and so on should be only applied to the assessments that are already assigned to Maintenance phase (on-treatment).

Long-term Follow-up phase assessments are assigned based on the LTFU study day as shown in Table 10. The analysis visits in LTFU should be only applied to the assessments that are already assigned to LTFU phase regardless of treatment state. See Section 12.6.1 for derivation of Maintenance and LTFU Study Day.

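### The SAP's injection-interval adherence summary uses one 60-day planned interval, so every on-schedule second injection, due at 30 days, is counted as more than 14 days early

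*SAP*

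**What the plan says.** SAP 12.6.2, under the heading on adherence to the injection schedule, sets a single constant: "The planned interval is 60 days for the CAB LA + RPV LA arm". Each interval is scored as "Relative Days=Actual number of days between adjacent injections – 60" and placed in categories that run from below -14 days to above 14 days, with separate rows for missed injections. On scope it states: "The injections of interest in adherence analysis are those after first injection". For the proportions, "the denominator is the total count of time intervals between adjacent injection visits for CAB LA + RPV LA arm". The exclusions it lists are extra unscheduled injections and double counting of the two drugs given at one visit. The loading interval is not among them.

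The same section also defines a timeliness measure, "actual injection visit date - projected visit date from first injection", which does not use the 60-day constant. For missed visits it says: "In the case that a scheduled injection visit is missed, the time interval between the preceding and the subsequent scheduled injection will be calculated". It gives no number of days at which a late visit becomes a missed one.

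Elsewhere the SAP fixes the schedule. Section 12.3.1 states that "the nominal target study day for Month m is ((m-1)\*30)+1 for Q2M". Table 6 in section 12.3.2 lists target days 1, 31 and 91 for Day 1, Month 2 and Month 4, and its note to Month 2 places the second loading injection one month after the first. Protocol 4.2.2 says the same.

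**The concern.** The 60-day constant matches the maintenance intervals but not the first one. If the loading interval is scored against 60 days, its scale is off centre by 30 days. A participant who receives every injection on its target day is then shown with one grossly early injection, so the summary cannot display full adherence.

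Direction is lost as well: a second injection that is moderately late still scores as early, and early, on-time and late second injections share one category. The protocol gives this injection its own dosing window in sections 4.2.2 and 6.8.1.1, yet the summary could not show departures from plan at that visit.

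The result would appear in Table 1.29 (SAP 12.12.4). Figure 3.17 (SAP 12.12.8), a histogram of injection timeliness, may use the projected-date measure. If it does, the two displays would disagree about the same injection.

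**Working it through.** **Inputs.** Planned interval 60 days, the scoring formula, the categories and the denominator: SAP 12.6.2. Target days: SAP 12.3.1 and Table 6. The first injection is on Day 1.

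**Plan's own figures.** Target day for Month m = (m - 1) × 30 + 1, giving Days 31, 91, 151, 211, 271 and 331 for Months 2 to 12. From Month 2 onward the differences are 91 - 31 = 60, 151 - 91 = 60, and so on, so the 60-day figure reproduces. The first worked example, 55 - 60 = -5, also reproduces. For the loading interval it does not: 31 - 1 = 30.

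The second worked example is inconsistent as printed: "if the interval is 60 days then relative days = 65 - 60 = 5". A 60-day interval gives 60 - 60 = 0; the printed result of 5 belongs to 65 days.

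**Perfect adherence to Month 12.** Intervals: 30, 60, 60, 60, 60, 60. Relative days: -30, 0, 0, 0, 0, 0.

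- Below -14 days: 1/6 = 16.7%.
- Within 7 days of plan: 5/6 = 83.3%.

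**Perfect adherence to Month 26 (Day 751).** There are 13 intervals, one of 30 days and twelve of 60.

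- Below -14 days: 1/13 = 7.7%.
- Within 7 days of plan: 12/13 = 92.3%.

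**Second injection on other days.** Interval = day - 1.

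| Day of second injection | Interval | Relative to 60 (as written) | SAP category | Relative to 30 |
|---|---|---|---|---|
| 24 | 23 | -37 | below -14 | -7 |
| 31 | 30 | -30 | below -14 | 0 |
| 38 | 37 | -23 | below -14 | +7 |
| 46 | 45 | -15 | below -14 | +15 |
| 47 | 46 | -14 | -14 to -8 | +16 |
| 60 | 59 | -1 | -1 | +29 |
| 61 | 60 | 0 | 0 | +30 |

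Every second injection up to 15 days late (Day 46) shares the lowest category with on-time and early ones. All those 1 to 29 days late (Days 32 to 60) score negative. One that is 30 days late scores exactly 0. The late cases in the table hold unless the visit is recorded as a missed injection.

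**With planned intervals of 30 then 60 days.** The on-schedule second injection scores 30 - 30 = 0, one given 7 days early scores 23 - 30 = -7, and every later on-schedule interval stays at 0.

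**The case against.** The best counter-reading is that the sentence limiting the analysis to injections after the first removes the first injection altogether. Intervals would then start at Month 2 to Month 4, every planned interval would be 60 days, and the constant would be right. This is coherent but is not what the text says. The second injection is itself after the first, the denominator counts all intervals between adjacent injection visits, and the loading interval is not among the listed exclusions. If exclusion was intended, the SAP has to state it.

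Three further points have some force and limit the finding:

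- The consequence is small. The summary is descriptive, no hypothesis is tested, the SAP's list of exploratory endpoints no longer includes injection adherence, and the projected-date measure handles the second injection correctly. The shell for Table 1.29 is not shown, so the programmed rows may differ from the text.
- The long delays in the table lie well outside the protocol's dosing window for this injection and might be recorded as missed. The SAP's Month 2 window of Days 2 to 60 is for slotting assessments and does not make a Day 60 injection timely.
- The second worked example looks like a typing slip, because the formula and the first example are clear. It needs correcting but adds little weight.

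None of these removes the central error, which arises for an injection given exactly on its target day.

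**Conclusion.** The concern holds. As written, SAP 12.6.2 classifies every on-schedule second injection as more than 14 days early. For a fully adherent participant this affects 1 of 6 intervals to Month 12 (16.7%) and 1 of 13 to Month 26 (7.7%), and the share within 7 days of plan reads 83.3% or 92.3% when the truth is 100%. Lateness of up to 29 days at the second injection is shown with a negative sign.

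The conclusion rests on the literal scope and denominator in 12.6.2, on the SAP's 30-day month for target days, and on Table 1.29 being programmed from that text. The primary ITT-E analysis does not change. This should be fixed because the stated rule gives a wrong answer for adherent participants and correcting it costs little.

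**What to change.** In SAP 12.6.2, replace the single constant with the SAP's own visit-specific planned intervals: 30 days for Day 1 to Month 2 and 60 days for each later pair. Correct the second worked example so that the stated interval and the arithmetic agree. State when a delayed visit counts as a missed injection.

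One related clarification concerns per-protocol criterion 02 in SAP 12.1.1. Its count of days beyond 67 between injections has no separate provision for the loading interval, so a second injection up to 67 - 30 = 37 days after target adds no non-compliant days automatically. Case-by-case review or criterion 05 could still catch it. The SAP should say whether this is intended, after the second-injection window in protocol 4.2.2 and 6.8.1.1 has been reconciled with footnote k of the Time and Events table, which gives 7 days in either direction.

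The cost is one or two lines of SAP text for the main change and a small programming edit. No new data are needed, and the dosing schedule does not change.

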## 12.6.3. **Efficacy**

#### **Snapshot**

- The Snapshot algorithm is intended to be primarily a virologic assessment of the endpoint, and as such follows a "virology first" hierarchy.
- 'HIV-1 RNA <50 c/mL' or 'HIV-1 RNA ≥50 c/mL' within an analysis window (see Table 8 and Table 9) is typically determined by the last available HIV-1 RNA measurement in that window while the subject is On-treatment in the Maintenance Phase (as assigned based on Section 12.4.1).

- When no HIV-1 RNA data is available within a window, a subject cannot be assigned to the

category of 'HIV-1 RNA < 50 c/mL'. Depending on the reason for lack of data, the subject will be classified as a 'HIV-1 RNA≥50' or reported as 'No Virologic Data at Month X'; in the latter case, the algorithm further classifies the nature of the missing data. Typically, a subject withdrawn (i) due to AE or, (ii) for another reason yet was suppressed at the time, will be counted as 'No Virologic Data at Month X'. Should a subject withdraw for reasons other than AE and was not suppressed at the time, they will be categorized as 'HIV-1 RNA≥50'.

- Full details of the algorithm, including the handling of special cases, are included in Section 12.9
- For each scheduled assessment time, the Snapshot response rate for a given threshold (e.g., <50 c/mL) is defined as:

Snapshot Response Rate= Number of responders in that analysis window Number of subjects in the analysis population

• For each scheduled assessment time, the Snapshot 'HIV-1 RNA≥50'rate for a given threshold (e.g., ≥50 c/mL) is defined as:

SnapshotVF Rate= Number of VFs in that analysis window Number of subjects in the analysis population

#### Plasma HIV-1 RNA

- For summaries and analyses which use HIV-1 RNA level as a continuous measure, the logarithm to base 10 of the value will be used.
- HIV-1 RNA results may be provided as censored values, such as <40 or >9,999,999 c/mL. For
  the purposes of summary statistics, such values will be replaced by the next value beyond the
  limit of detection, e.g., 39 or 10,000,000 c/mL, respectively, for the given examples. Data
  listings will show the censored values as provided.

## Target Detected / Target Non Detected/Super low viral load testing

- When a measurement of plasma HIV-1 RNA is below the limit of quantification (i.e. 40 c/mL) and is qualitatively observable that will be denoted as a "Target Detected" measure, while HIV-1 RNA below the limit of quantification that is not qualitatively observable that will be denoted as "Target Not Detected". Any measurements <40 c/mL characterised as "Target Non Detected" or "Target Detected" will be captured in the database.

- Super low viral load will also be tested by BioMNTR lab for Viral loads below the limit of quantification at some visits (e.g. Month 12)

### **Confirmed Virologic Failure (CVF)**

- The definition of CVF is provided in the Protocol, Section 7.1.4 Definition of Protocol-Defined Confirmed Virologic Failure
- In case there are multiple plasma HIV-1 RNA results on the same day, the worst result (i.e. the largest value) will be used in determination of CVF.

### Summary for Participants per Viral Load Category by Visit

- Summary will be based on observed available data, with no imputation for missing values. The
  proportion of participants in each viral load category will be calculated using the denominator
  and numerator specified below:
  - Denominator: Number of participants with on-treatment viral load within the snapshot visit window.
  - Numerator: Number of participants with plasma HIV-1 RNA in the specified category based on the last on-treatment viral load assessment collected within the snapshot visit window.

## **HIV-1 Disease progression Stage**

- Categories:
  - CDC Stage I at Maintenance Baseline to CDC Stage III;
  - CDC Stage II at Maintenance Baseline to CDC Stage III;
  - CDC Stage III at Maintenance Baseline to new CDC Stage III event and
  - CDC Stage I, II, III at Maintenance Baseline to death.

Please refer to Protocol (Appendix 8: CDC Classification for HIV-1 Infection (2014)) for defining Stage.

- For the purpose of analysis, the CDC at Baseline and at post-baseline during Maintenance phase will be derived as below:
  - At Baseline, the 'Baseline CDC stage' for each subject was assessed by the investigator and recorded in the eCRF. However, for the analysis, Maintenance Baseline CDC stage will be re-derived based on Maintenance Baseline CD4+ values as well as whether any HIV-associated conditions present at Baseline per the Criteria's thresholds (Appendix 8 in Protocol).
  - To analyse disease progression, the most advanced post-baseline CDC stage within the period of interest (e.g. Maintenance Phase) will be derived based on the occurrences of new AIDS-defining conditions (please refer to Appendix 8 in Protocol for the list of AIDs-defining Conditions) as well as the nadir value of Maintenance CD4+. For example,
    - If a subject with CDC 'Stage I' at Maintenance Baseline had the lowest Maintenance Phase CD4+ =120 cell/mm³ without new AIDs-defining conditions, then HIV disease progression for this subject during the Maintenance phase would be considered as 'CDC stage I at Baseline to CDC stage III'.
    - If a subject with CDC 'Stage II' at Baseline had the lowest Maintenance Phase CD4+ =220 cell/mm³ AND had at least one new AIDs-defining condition, then HIV disease progression for this subject during the Maintenance Phase would be considered as 'CDC stage II at Baseline to CDC stage III'.

## 12.6.4. Safety

#### **Adverse Events**

#### **DAIDS Grading**

 Clinical adverse events will be graded based on the Division of AIDS Table for Grading the Severity of Adult and Pediatric Adverse Events Version 2.1, March 2017, as specified in the protocol Appendix 2.

## Potential QTc Interval Prolonging Events of Interest

Potential QTc Interval Prolonging Events of Interest cases will be identified based on Standardised MedDRA Query (SMQ) for Torsade de pointes/QT prolongation, broad (MedDRA). The terms per this reference are listed below.

#### AE preferred term

Adverse Events	
Electrocardiogram QT interval abnormal	
Electrocardiogram QT prolonged	
Long QT syndrome	
Long QT syndrome congenital	
Torsade de pointes	
Ventricular tachycardia	
Cardiac arrest	
Cardiac death	
Cardiac fibrillation	
Cardio-respiratory arrest	
Electrocardiogram repolarisation abnormality	
Electrocardiogram U wave inversion	
Electrocardiogram U wave present	
Electrocardiogram U-wave abnormality	
Loss of consciousness	
Sudden cardiac death	
Sudden death	
Syncope	
Ventricular arrhythmia	
Ventricular fibrillation	
Ventricular flutter	
Ventricular tachyarrhythmia	

### **Laboratory Parameters**

- If a laboratory value which is expected to have a numeric value for summary purposes, has a non-detectable level reported in the database, where the numeric value is missing, but typically a character value starting with '<x' or '>x' (or indicated as less than x or greater than x in the comment field) is present, the number of significant digits in the observed values will be used to determine how much to add or subtract in order to impute the corresponding numeric value. If a character value starting with "<=x", then the numeric value will be x.
  - $\circ$  Example 1: 2 Significant Digits = '< x ' becomes x 0.01
  - Example 2: 1 Significant Digit = '> x' or '>=x' becomes x + 0.1
  - Example 3: 0 Significant Digits = '< x' becomes x 1

## Estimate of Glomerular Filtration Rate (GFR) (Levey, 2012)

• Chronic Kidney Disease Epidemiology Collaboration (CKD-EPI) equation [Levey, 2012].will be used by the central laboratory to provide an estimate of GFR, in mL/min per 1.73 m², as follows:

#### **Laboratory Parameters**

GFR = 
$$141 \times \min \left(\frac{\text{CRT}_{\text{mg/dL}}}{\kappa}, 1\right)^{\alpha} \times \max \left(\frac{\text{CRT}_{\text{mg/dL}}}{\kappa}, 1\right)^{-1.209} \times 0.993^{\text{Age}} \times [1.018 \text{ if Female}] \times [1.159 \text{ if Black}]$$

where age (in years) is at time of assessment,  $\kappa$  = 0.7 if female or 0.9 if male,  $\alpha$  = -0.329 if female and -0.411 if male, min() indicates the minimum of CRT/ $\kappa$  or 1, max() indicates the maximum of CRT/ $\kappa$  or 1, and CRTmg/dL is serum creatinine concentration in mg/dL. The serum creatinine concentration in mg/dL is obtained from GSK standard units of  $\mu$ mol/L as CRTmg/dL =0.0113x CRT $\mu$ mol/L.

• The CKD-EPI GFR will also be calculated using Cystatin C, as follows

133 X min(Scys/0.8, 1) -0.499 X max (Scys/0.8, 1)-1.328 X 0.996 Age X[0.932 if female]

Where Scys is serum cystatin C mg/Liter, min indicates the minimum of Scr/0.8 or 1, and max indicates the maximum of Scys/0.8 or 1

# Lab Toxicities – DAIDS Grading based on Version 2.1, March 2017, as specified in the protocol of Appendix 2

- Toxicities will be based on the Division of AIDS (DAIDS) grading system, Version 2.1, March 2017, as specified in the protocol of Appendix 2.
- Toxicity grades provided by the central laboratory do not distinguish between abnormally high or low criteria, when both are relevant for a particular parameter.
- When summarising toxicity grades for such parameters, they will be categorised as to whether they are above or below the midpoint of normal range.

Parameter	Below Midpoint for those ≥Grade 1	Above Midpoint for those ≥Grade 1
Fasted glucose	Hypoglycemia	Hyperglycemia
Sodium	Hyponatremia	Hypernatremia
Potassium	Hypokalemia	Hyperkalemia

